13 STATISTICS AND DATA ANALYSIS

Detailed methodology for summaries and statistical analyses of the data collected will be documented in a separate Statistical Analysis Plan (SAP) that will be finalized before database lock. Any changes to the methods described in the final SAP will be described and justified as needed in the Clinical Study Report (CSR).

This section describes the general framework to be used for the analysis and presentation of data in this study. The information described in this section may be revised during the study to accommodate protocol amendments and to make changes to adapt to unexpected issues in study execution and data that could affect planned analyses. All available data will be included in data listings. Data tabulations will be performed for specific analysis populations. No imputation of values for missing data will be performed.

Statistical analyses will be primarily descriptive; no formal hypothesis testing will be conducted. Descriptive statistics will be provided for selected baseline, safety, and efficacy data by dose level and time point as appropriate.

In general, clinical data will be summarized for the dose escalation cohorts and for the dose expansion cohort, separately by each dose level where applicable, using descriptive statistics. Descriptive statistics for continuous data will include means, medians, standard deviations, and ranges, while categorical data will be summarized using frequency counts and percentages. Graphical presentation of selected data may also be performed. Non-zero percentages will be rounded to one decimal place, except 100% will be displayed without any decimal places. For selected assessments, confidence intervals (CIs) will be displayed.

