13.1 Sample Size Considerations

Estimated sample sizes are calculated for the two primary outcome measurements: ADAS-Cog and GM atrophy (hippocampal). In order to ensure that the study has sufficient power to detect differences in both of the primary outcomes, the sample size chosen is the maximum of that calculated for each primary outcome.

The primary analysis was an intention-to-treat analysis and included all randomized participants. Data will be analysed using both Generalised Estimating Equations (GEE) and Bayesian Analysis.

The analysis of primary endpoints will use linear mixed-effects models, with random slopes and intercepts. For the ADAS-Cog, using mixed model analysis published estimates from the ADNI cohort¹⁷ suggest a sample size of 125 AD participants per trial arm (total N = 250) will be required for power at 0.8 to detect a drug effect of 25% over two years and assuming a decline from baseline of 1.10 standardised units on the composite (SD change = 0.83).

Protocol Version 4, 06 OCT 2021

Confidential

Page 49 of 70

Curtin University Study Protocol
Protocol No.: PIA-2020

For the MRI markers, Ledig *et al.* reported the sample sizes required for a 25% intervention reduction over two years based on 322 patients with AD (with 117 followed for 24 months) and a reduction of 10.2% (6.2) for hippocampus¹⁸. Sample size calculations based on hippocampal volume suggest that 93 subjects per treatment arm are required (total N = 186).

Assuming a 20% attrition rate, a sample of 314 subjects will be recruited for the Cognitive study, and 233 subjects will be randomly chosen for the Imaging study.

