13.6 Efficacy Analyses

The primary analysis was an intention-to-treat analysis of all randomized participants. Data will be analysed using both Generalised Estimating Equations (GEE) and Bayesian Analysis. The analysis of primary endpoints will use linear mixed-effects models, with random slopes and intercepts.

The Alzheimer's Disease Assessment Scale's cognitive subscale (ADAS-Cog) is the standard primary cognitive outcome measure for evaluating treatments in clinical trials of mild-to-moderate AD. But the utility of ADAS-Cog is compromised primarily due to some of its items suffering from either floor or ceiling effects in different stages of AD. The current scoring methodology is also sensitive to missing item responses, scoring errors and variability in the administration of the ADAS-Cog, which are common in clinical trials.

The scoring methodology ADAS-Cog as proposed by Verma et al. will be utilised as it significantly improves the sensitivity of the ADAS-Cog in measuring progression of cognitive impairment in clinical trials focused in the mild-to-moderate AD stage²¹. This scoring methodology also provides a boost to the efficiency of clinical trials requiring fewer patients and shorter durations for investigating disease-modifying treatments. For patients with missing responses to certain items, this new scoring methodology does not require data imputation and estimates cognitive impairment using the set of items answered by the patients.

Analysis of all primary and secondary endpoints contrasting Probucol and placebo, after adjusting for covariates, will use mixed effects-regression with 'random' intercepts and slopes (as has been used for power calculations). Mean differences and associated 95% confidence intervals will be presented for the 'fixed' effect of Probucol treatment.

Further analysis investigating the relationship between change scores (post-minus pre-intervention scores) for the primary ADAS-Cog with MRI volumes (total GM, hippocampus, and medial temporal lobe volumes) and specific blood biomarkers (eg: plasma lipoprotein-Aβ) will be considered using Pearson (or Spearman where appropriate) correlation analysis. For all other correlations between recorded variables that lack an a priori hypothesis, control of statistical errors will be carried out using Holm-Sidak corrections for multiple comparisons.

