If Probucol treatment is successful, a directed acyclic graph Bayesian network analysis will be carried out a posteriori on variables identified to be significant predictors of either GM arrest or neuropsychological performance to better elucidate mechanisms of the effect of Probucol. Greedy equivalence search will be used to identify statistical conditional dependencies between variables and directionality will be estimated using the linear, non-Gaussian, acyclic causal models (LiNGAM) approach^{22,23}. Goodness of fit will be estimated using a $\chi 2$ test contrasting the identified model against a saturated model.

In addition to Bayesian analyses, the traditional General Linear Model analysis will also be utilised to compare Probucol to placebo, after adjusting for covariates. The Generalized

Protocol Version 4, 06 OCT 2021

Confidential

Page 51 of 70

Estimating Equations method, which extends the generalized linear model to allow for analysis of repeated measurements or other correlated observations, will also be utilised.

Mean difference and associated 95% confidence intervals will be presented. Data will be analysed using Stata Version 16.

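### Section 13 rules out formal hypothesis testing, but the trial is sized at 80% power and acts on 'success', and the standing of the GEE, Bayesian and general linear model analyses beside the mixed model is not stated

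*Protocol*

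**What the plan says.** **Testing.** The opening of Section 13 states: "Statistical analyses will be primarily descriptive; no formal hypothesis testing will be conducted". The sentence has no qualifier, and the one after it includes efficacy data among what will be described. The same section says that "clinical data will be summarized for the dose escalation cohorts and for the dose expansion cohort".

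**Sizing.** Section 13.1 (repeated in Section 7.1) says that 125 participants per arm "will be required for power at 0.8 to detect a drug effect of 25% over two years". It refers to two primary outcomes, ADAS-Cog and hippocampal atrophy. For the hippocampus it gives 93 per arm.

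**Methods for probucol versus placebo.** Section 13.6 says: "The analysis of primary endpoints will use linear mixed-effects models, with random slopes and intercepts". It adds that all primary and secondary endpoints will be contrasted by mixed-effects regression, as in the power calculation, and that "Mean differences and associated 95% confidence intervals will be presented for the 'fixed' effect of Probucol treatment". The same section also says: "Data will be analysed using both Generalised Estimating Equations (GEE) and Bayesian Analysis". Later it says: "In addition to Bayesian analyses, the traditional General Linear Model analysis will also be utilised to compare Probucol to placebo", with GEE named again.

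**Decision language.** Section 13.6 says: "If Probucol treatment is successful, a directed acyclic graph Bayesian network analysis will be carried out". That network is to be built on variables found to be significant predictors. The section also applies Holm-Sidak corrections to correlations that have no prior hypothesis.

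**The concern.** Power is the probability that a stated test at a stated alpha rejects. If no test will be done, the 80% has no referent, and the basis for recruiting 314 people is undefined. The protocol nevertheless acts on success without saying what success is, and Section 6.1 expects strong results to support phase III trials.

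This is more than detail left to a SAP. A SAP that named a primary test and alpha would contradict an explicit protocol sentence, so the correction belongs in the protocol.

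The second part is the standing of the other methods. A reader can see that the mixed model leads, but not whether a disagreeing GEE, general linear model or Bayesian result would alter the conclusion.

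**Working it through.** **1. Does the sizing presuppose a test?** Inputs for the hippocampus from Section 13.1: reduction 10.2%, bracketed 6.2 (read as the SD), intervention effect 25%, 1:1 allocation (Section 6.1). The protocol states no alpha or sidedness, and gives the power of 0.8 only with the ADAS-Cog figure. I try 80% here too.

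- δ = 0.25 × 10.2 = 2.55.
- n per arm = 2 (z₁₋α/₂ + z₀.₈₀)² (SD/δ)².
- Two-sided 5% (the same as one-sided 2.5%): 2 × 7.849 × (6.2/2.55)² = 2 × 7.849 × 5.912 = 92.8, so **93**, the stated figure.
- One-sided 5%: 2 × 6.183 × 5.912 = 73.1, so 74, which does not match.

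The stated 93 is therefore the sample size for a two-sided 5% test with 80% power.

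**2. ADAS-Cog.** δ = 0.25 × 1.10 = 0.275 and SD = 0.83. The same formula gives 2 × 7.849 × 9.109 = 143 per arm, against the stated 125. I do not rely on this difference. The protocol attributes 125 to published mixed-model estimates whose variance components it does not give, and repeated measures can lower the number.

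**3. Places in Section 13 set side by side.**

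| Place | Content | Consistent with no formal testing? |
|---|---|---|
| 13, opening | Descriptive only, no tests | – |
| 13.1 (and 7.1) | Sized at power 0.8 | No |
| 13.6 | Holm-Sidak corrections | No: they adjust tests |
| 13.6 | Significant predictors | No |
| 13.6 | Step conditional on success | No: success needs a rule |

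**4. Cohorts.** The opening of Section 13 summarises by escalation and expansion cohorts. Section 6.1 defines a two-arm 1:1 trial with one planned dosing schedule (Table 2). Its initial thirty single-patient cohorts, and the possible further 30 patients at the same dose level, are an early safety step. They are not called escalation or expansion cohorts. The Synopsis mentions intermediate doses only as an option.

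**5. Rank of the methods.**

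- *Mixed model:* tied to the primary endpoints, to all primary and secondary contrasts, and to the power calculation, with a mean difference and 95% interval.
- *GEE and Bayesian analysis:* named directly after the sentence on the primary intention-to-treat analysis and before the mixed model, as methods that will both be used.
- *General linear model:* added for the same comparison.

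The mixed model is ahead, but none of the others is labelled supportive or sensitivity.

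**6. Illustration of what an open choice could cost.** Suppose, contrary to anything the protocol states, that success could be claimed if any of three frequentist tests (mixed model, GEE, general linear model) reached two-sided 0.05. Let the test statistics be equicorrelated normals with correlation r under no effect. Then

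P(any) = 1 − ∫ φ(u) [Φ((1.96 − √r·u)/√(1−r)) − Φ((−1.96 − √r·u)/√(1−r))]³ du.

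| r (assumed) | P(any of three) |
|---|---|
| 0.80 | 9.8% |
| 0.90 | 8.4% |
| 0.95 | 7.3% |

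**The case against.** The strongest reply is that the mixed model is already primary in substance. Section 13.6 and the Synopsis tie it to every primary and secondary contrast, and GEE and the general linear model come later as additions. Alpha, a success rule and sensitivity labels commonly sit in a SAP, which Section 13 promises before database lock. Much of this stands, and it rules out several stronger readings that a reader might infer:

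- *That no method leads, so no single result could decide.* Too strong. The order of methods is unclear, not absent.
- *That four rival methods test the same contrast.* Not established. The only Bayesian analysis described is the post hoc network on mechanism; whether a Bayesian treatment comparison is also planned is ambiguous.
- *That GEE and the general linear model need data missing completely at random, while the mixed model does not.* The protocol does not say that GEE is unweighted or that the general linear model uses change scores. Change scores appear only for the correlation analyses.
- *That the error rate is inflated, or that the sponsor may report the most favourable result.* The protocol contains no any-of-several rule, and the SAP is not at hand.
- *That the trial has no cohorts at all.* Section 6.1 does describe initial single-patient cohorts.

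The reply does not rescue the sentence that rules out formal testing. It is a positive statement in the protocol, at odds with the protocol's own sizing and decision language.

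**Conclusion.** The point holds in this form: the statement that no formal hypothesis testing will be conducted is wrong as written, because Sections 7.1, 13.1 and 13.6 presuppose tests. This part rests on the text and on one reproduced figure (93 per arm, reading 6.2 as an SD and taking 80% power). The escalation and expansion cohorts have no definition in the design. It is also true, with less force, that the GEE, general linear model and any Bayesian comparison have no stated standing beside the mixed model, and that success is undefined.

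The 7.3% to 9.8% range is illustrative. It depends on an assumed rule, assumed correlations and an assumed two-sided 0.05, and is not an estimate of this trial's error rate.

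Two neighbouring inconsistencies must be settled at the same time, or a named primary analysis would still not give one answer. Sections 7.1 and 13.1 have two primary outcomes, while Section 5 lists only ADAS-Cog as primary. Section 13.2 assigns all efficacy analyses to patients who received Lorelco, which leaves out the placebo arm and conflicts with the intention-to-treat analysis in Section 13.6.

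**What to change.** 1. Delete the sentence in Section 13 that excludes formal testing.
2. Delete the escalation/expansion cohort sentence, or reconcile it with the initial cohorts in Section 6.1.
3. State in Section 13.6: *The primary analysis is the treatment effect on ADAS-Cog over the treatment period from the linear mixed model with random intercepts and slopes, in all randomised participants, at two-sided alpha 0.05. Success means that this test is significant in favour of probucol. Hippocampal volume is secondary. GEE, the general linear model and any Bayesian treatment comparison are sensitivity analyses and do not change the primary conclusion.* The SAP can then name the exact model contrast (difference in slope, or estimated difference at week 104).
4. Align Sections 7.1 and 13.1 with Section 5 on the number of primary outcomes.
5. In Section 13.2, replace the Lorelco-only population for efficacy analyses with all randomised participants.

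The cost is protocol wording. No planned method is dropped and no data collection changes. Because it touches the science of the study, Section 18.3 would probably class it as a substantial amendment needing ethics committee approval. It should be in place before database lock and unblinding.

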13.1 Sample Size Considerations

Estimated sample sizes are calculated for the two primary outcome measurements: ADAS-Cog and GM atrophy (hippocampal). In order to ensure that the study has sufficient power to detect differences in both of the primary outcomes, the sample size chosen is the maximum of that calculated for each primary outcome.

The primary analysis was an intention-to-treat analysis and included all randomized participants. Data will be analysed using both Generalised Estimating Equations (GEE) and Bayesian Analysis.

The analysis of primary endpoints will use linear mixed-effects models, with random slopes and intercepts. For the ADAS-Cog, using mixed model analysis published estimates from the ADNI cohort¹⁷ suggest a sample size of 125 AD participants per trial arm (total N = 250) will be required for power at 0.8 to detect a drug effect of 25% over two years and assuming a decline from baseline of 1.10 standardised units on the composite (SD change = 0.83).

Protocol Version 4, 06 OCT 2021

Confidential

Page 49 of 70

Curtin University Study Protocol
Protocol No.: PIA-2020

For the MRI markers, Ledig *et al.* reported the sample sizes required for a 25% intervention reduction over two years based on 322 patients with AD (with 117 followed for 24 months) and a reduction of 10.2% (6.2) for hippocampus¹⁸. Sample size calculations based on hippocampal volume suggest that 93 subjects per treatment arm are required (total N = 186).

Assuming a 20% attrition rate, a sample of 314 subjects will be recruited for the Cognitive study, and 233 subjects will be randomly chosen for the Imaging study.

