6 STUDY DESIGN

6.1 Design Type and Description

This is a Phase 2, randomised, double blind, placebo-controlled parallel group study in adults with mild to moderate AD.

The study will assess the efficacy, safety and tolerability of the treatment of Alzheimer's disease in approximately 300 subjects with LorelcoTM.

After consenting to participate in the study, screening procedures will occur between Days - 24 and -1. All subjects must have measurable mild or moderate Alzheimer's disease, and accordingly screening procedures will include:

- o A positive amyloid biomarker (PET scan) indicative of AD pathology,
- o Mini-mental-state examination (MMSE) score of 22 or greater,
- Free and cued selective reminding test (FCSRT) cueing index of 0.79 or less OR free recall score ≤17
- o Clinical Dementia Rating (CDR) global score of 0.5 or 1.0.
- o A study partner (partner/spouse/carer) consents to the minimum requirements:
 - Study partner will attend at least one screening visit
 - Study partner will be available via phone or in person to provide information to the study as required

Eligible subjects will be randomized in a 1:1 (active:placebo) ratio and return to the study unit on Day 1.

The dosing schedule for subjects is shown in Table 2. The two week initial placebo period will allow for implementation and retraining to assist with dose compliance, without giving participants the intervention drug. The dose level and regime begins at 250 mg a day (Week 3) to monitor for gastrointestinal safety events.

Table 2. Planned Subject Dosing Schedule

Week	Dose Level	Total Daily Lorelco TM Dose (mg)
Week 1 and 2	1 x placebo taken in the morning, with food.	0 mg
Week 3	1 x 250 mg Lorelco [™] (or matching placebo) taken in the morning, with food.	250 mg (or placebo 0 mg)
Week 4 -104	 1 x 250 mg probucol (or matching placebo) taken in the morning, with food. 1 x 250 mg probucol (or matching placebo) taken in the evening, with food. 	500 mg (or placebo 0 mg)

Subjects will self-administer LorelcoTM or placebo in the clinic under the supervision of site staff on Days 1 (±2 days) on Weeks 1, 2, 3, 4, 5, 15, 26, 39, 52, 65, 78 and 104. All other doses will be self-administered at home, or under the supervision of the designated study partner as appropriate. LorelcoTM and Placebo will be provided in a Webster pack or equivalent to assist with dose compliance.

[figure not shown]

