11.6.2 Primary Cognitive Assessment

Alzheimer's Disease Assessment Scales-Cognitive Subscale test (ADAS-Cog)¹⁷: The Alzheimer's Disease Assessment Scale-Cognitive Subscale test (ADAS-Cog) is the most widely used test to measure cognition in RCT's for AD. Taking 30 to 40 minutes to administer it is commonly used in clinical trials as it can determine incremental improvements, or decline

Protocol Version 4, 06 OCT 2021

Confidential

Page 39 of 70

in cognitive functioning. The ADAS-Cog12 version consists of the following tasks: Word Recall Task; Following Commands; Constructional Praxis; Delayed Word Recall; Naming Objects and Fingers; Ideational Praxis; Orientation; Word Recognition; Spoken Language; Comprehension and Word Finding Difficulty. Inclusion of the delayed word recall component has shown an increased ability to detect change in the MCI population. Sensitivity of ADAS-Cog is indicated by a scoring differential of approximately six-fold in patients with the earliest manifestation of AD compared to aged-matched health controls. The full suite of ADAS-Cog will be at baseline, 26, 52, 78 and 104 weeks.

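### The 80% power rests on inputs from an undefined standardised composite and cannot be tied to the ADAS-Cog score that will be analysed

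*Protocol*

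**What the plan says.** Section 13.1, repeated in 7.1, introduces the calculation with "For the ADAS-Cog, using mixed model analysis published estimates from the ADNI" cohort. It says these estimates "suggest a sample size of 125 AD participants per trial arm (total N = 250") for "power at 0.8 to detect a drug effect of 25% over two years", "assuming a decline from baseline of 1.10 standardised units on the composite (SD change = 0.83"). Allowing for 20% attrition, 314 participants are to be recruited.

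The rest of the protocol describes the primary measure in other terms:

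- Section 5 lists the ADAS-Cog as the cognitive endpoint, in a list left open to additions.
- Section 11.6.2 fixes the item set: "The ADAS-Cog12 version consists of the following tasks".
- Section 13.6 adopts a published scoring method because of its better sensitivity to progression, and adds: "This scoring methodology also provides a boost to the efficiency of clinical trials requiring fewer patients and shorter durations".
- Section 13.6 also says the mixed-effects model is the one used for the power calculation. That sentence links the model to the calculation. It does not link the score.

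**The concern.** The word composite occurs only in the duplicated sample-size sentence. Nothing says what the composite contains, how it is scored, or what its units are standardised to. The primary analysis will use an ADAS-Cog score under the 13.6 method, and no passage says that the 1.10 and 0.83 were obtained under that method.

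This matters because the effect is set as a percentage of the expected decline. Power then depends on how large that decline is relative to its SD, and two ways of scoring the same items can differ in that ratio. Section 13.6 says as much when it claims that its scoring reduces the number of patients needed. At stake is the justification for 125 per arm, and so for recruiting 314. The cognitive calculation drives the trial size, since the hippocampal one needs only 93 per arm.

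**Working it through.** **Inputs**

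- From 13.1: decline 1.10, SD of change 0.83, effect 25%, power 0.80, 125 per arm, attrition 20%.
- From 6.1: "Eligible subjects will be randomized in a 1:1 (active:placebo) ratio".
- Alpha is not stated for the calculation. I assume 0.05 two-sided, in line with 13.6: "Mean differences and associated 95% confidence intervals will be presented for the" treatment effect.

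**The protocol's own figure**

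- Difference to detect: 0.25 × 1.10 = 0.275.
- Standardised difference: 0.275 / 0.83 = 0.331.
- Patients per arm: 2 × (1.960 + 0.842)² / 0.331² = 143 (144 with the t distribution), against 125 stated.
- Power at 125 per arm: Φ(0.331 × √(125/2) − 1.960) = Φ(0.659) = 74.5%.
- One-sided 5%: 113 per arm, and 83.5% power at 125. Other common choices of alpha and power did not give 125 either.
- SD that 125 per arm would need at two-sided 5%: 0.275 × √62.5 / 2.802 = 0.776. That is a variance lower by 1 − (0.776/0.83)² = 12.6%.

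A repeated-measures mixed model could supply a gain of that size, so 125 is not shown to be wrong. Its variance components are not in the protocol, so it cannot be confirmed.

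**Neighbouring figures, same method**

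- Hippocampus: difference 0.25 × 10.2 = 2.55, SD 6.2, giving 93 per arm. This reproduces and supports the assumed alpha.
- Attrition: 125 / 0.8 = 156.25, rounded up to 157 per arm, or 314 in total. This reproduces.

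**Dependence on the score**

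With r the mean decline divided by the SD of change, a 25% effect gives

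power at 125 per arm = Φ(0.25 × r × √62.5 − 1.960)

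n per arm for 80% = 2 × 2.802² / (0.25 × r)²

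| r | n per arm for 80% | Power at 125 per arm |
|---|---|---|
| 0.8 (assumed) | 393 | 35% |
| 1.0 (assumed) | 252 | 51% |
| 1.2 (assumed) | 175 | 66% |
| 1.325 (1.10/0.83, protocol) | 143 | 74.5% |
| 1.5 (assumed) | 112 | 84% |

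The protocol gives no ratio for the ADAS-Cog under the 13.6 scoring, so the assumed rows only show the range.

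If the mixed model is credited with exactly the gain that makes 1.325 yield 80%, power becomes Φ(2.802 × r/1.325 − 1.960). The assumed ratios then give 39%, 56%, 72% and 89%. The dependence on the score remains.

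**Citations**

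The estimates in 13.1 carry reference 17. The scoring method carries reference 21 in 13.6 and 19 in the synopsis. Reference 17 in the list is, by its title, a paper on adding delayed recall to the scale, and 11.6.2 cites it for the instrument. Its title mentions neither the cohort nor a composite. A reader cannot identify the composite from the protocol.

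**The case against.** The strongest reply is that the sentence itself says the calculation is for the ADAS-Cog, and 13.1 names the ADAS-Cog as the outcome being sized. The composite may simply be a standardised ADAS-Cog score from the cited publication. This stands to the extent that a reader might infer that the trial was powered on a different endpoint, and the documents do not show that. The scoring of the composite is not stated, so they show neither that it differs from the 13.6 score nor that it matches.

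Three further points also stand:

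- The 12-item version and the 13.6 scoring rule are compatible, one being an item set and the other a way of scoring it. They are not rival definitions of the endpoint.
- A reader might infer that the trial is underpowered. If the new scoring is as sensitive as 13.6 says, its ratio could exceed 1.325 and power could be higher than planned.
- The shortfall from 80% to 74.5% comes from a simple comparison of changes, whereas the protocol cites a mixed model. It does not prove an error in 125.

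It could also be said that section 13 describes the analyses as mainly descriptive, without formal hypothesis tests, so that power matters less. That does not help, because 7.1 and 13.1 still claim 80% power and derive the recruitment target from it. Nor can a later analysis plan settle it, since the basis for the sample size is stated here.

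**Conclusion.** The point holds as a failure to connect the power claim to the endpoint. The protocol states 80% power on inputs from a measure it never defines, and fixes for the analysis a scoring method that it says alters the required sample size. Nothing joins the two. The inputs as printed also do not give 125 per arm by a simple two-sided 5% comparison (143 needed, 74.5% power at 125), and the quantities that might explain the difference are absent.

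The size of any error cannot be computed from the protocol and its direction is unknown. Over assumed ratios of 0.8 to 1.5, power at 125 per arm runs from 35% to 84%. These figures rest on a two-sided 5% level, 125 analysable participants per arm and a comparison of two-year changes.

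**What to change.** In 7.1 and 13.1, do one of two things: show that the composite is the ADAS-Cog12 under the 13.6 scoring, or replace 1.10 and 0.83 with the mean and SD of two-year change on that score. State alpha and sidedness, give the mixed-model variance inputs, cite the source of the estimates correctly, and restate power at the planned size.

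Name that same score as the single primary variable in sections 5, 11.6.2 and 13.6. The status of hippocampal atrophy, which 13.1 also calls a primary outcome, is a separate matter. A supportive analysis of the conventional ADAS-Cog total is optional.

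The cost is protocol wording and one recalculation. Restating power at the planned size adds no patients in itself. The downside is that the figure may turn out less favourable than 80%, and the sponsor would then have to decide openly whether to accept it.
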